3.2 Additional Devices

Additionally, only the following **Stryker compatible** devices may be used, according to this study protocol:

Required Additional Components			
5512-F-XXX	Triathlon TS Femoral Component		
5521-B-XXX	Triathlon TS Universal Tibial Baseplate		

Study Specific Tibial Inserts			
5537-G-XXX	Triathlon TS Tibial Insert		
5532-G-XXX	Triathlon PS Tibial Insert, X3		
5532-P-XXX	Triathlon PS Tibial Insert, N2Vac		

Optional Ancillary Devices				
5550-G-XXX	Triethlan Datellar Component Symmetric	X3		
5550-L-XXX	That non Patellar Component, Symmetric	N2Vac		
5551-G-XXX	Triethlen Beteller Component Asymmetrie	X3		
5551-L-XXX	Thatmon Patellar Component, Asymmetric	N2Vac		
5565-S-XXX	Triothlan Flutad Stam	100 mm		
5566-S-XXX	Thatmon Fluted Stem	150 mm		
5560-S-XXX	Triathlon Cemented Stem			
5571-S-XXX	Triathlon Stem Extender			

CONFIDENTIAL

This material is the property of Stryker Orthopaedics. Do not disclose or use except as authorized in writing by Stryker.

5570-S-XXX	Triathlon TS Offset Adapter	
5540-A-XXX	Triathlon Femoral Distal Augment	5 mm
5541-A-XXX		10 mm
5542-A-XXX		15 mm
5543-A-XXX	Triathlon Femoral Posterior Augment	5 mm
5544-A-XXX		10 mm
5545-A-XXX	Triathlan Tibial Llaff Black Augment	5 mm
5546-A-XXX		10 mm
5540-A-000	Triathlan Comaral Augment Leaking Corour	
5545-A-000	That non Femoral Augment Locking Sciew	

The compatible Stryker components are listed in the surgical protocol and Appendix B.

In the case of any uncertainty regarding device compatibility, the current version of the Triathlon TS surgical protocol should be reviewed.

4 Study Procedures

4.1 Subject Recruitment and Screening

Patients will be recruited at the study centers during preoperative visits through normal referral patterns. Advertising for the study at each center will be at the discretion of the investigator. All handouts, brochures, advertisements, etc. must be approved by the IRB/EC prior to the dissemination of any recruitment materials to potential subjects. Study advertisement content may be found in Appendix C.

During the preoperative visit, patients that are possible candidates for this study will be screened to determine if they meet the inclusion/exclusion criteria. If the patient is a candidate, the investigator will propose participation in the study to the patient, according to GCP guidelines. Patients must sign an IRB/EC approved Informed Patient Consent Form prior to participation in the study, as well as prior to any data collection.

4.2 Patient Informed Consent and Guidelines

All patients for this study will be provided an Informed Patient Consent Form describing this study and providing sufficient information for them to make an informed decision about their participation. The Informed Patient Consent Form must contain all elements required by the FDA under 21 CFR Part 50, in addition to any other elements required by state, local and institutional policies. For international sites, the applicable country regulations are required. See Appendix D for a copy of the Model Informed Patient Consent. This will be submitted with the protocol for review and approval by the IRB/EC for the study. All patients must provide written consent after having had adequate time to consider their participation in the study. The formal consent of a patient, using the IRB/EC approved Informed Patient Consent Form, must be obtained before that patient is submitted to any protocol related procedures that are not part of normal care. Written documentation of consent must be provided on the Informed Patient Consent Form's signature page in addition to a note in the patient medical records indicating the date that consent was obtained. The investigator-designated research professional obtaining the consent must also sign this Informed Patient Consent Form. The patient or his/her legal representative should receive a signed copy of the Informed Patient Consent Form, according to GCP guidelines.

The procedure for obtaining informed consent is outlined below:

- Use a current IRB/EC approved copy of the Informed Patient Consent Form.
- Review thoroughly with the patient, allowing adequate time to consider participation in the study and ask questions, before having them sign.
- After the patient has consented to the procedures, ensure he/she signs and dates the Informed Patient Consent Form.
- The person obtaining consent also signs and dates the signature page.
- Provide a copy of the Informed Patient Consent Form to the patient.
- If required, provide the hospital with a copy of the signed Informed Patient Consent Form.
- Maintain the signed original in the patient's study chart.

4.3 Early Withdrawal of Subjects

When and How to Withdraw Subjects

In the event that the subject is discontinued by the investigative center prior to the final study evaluation, the subject will be notified by the center that he/she is no longer in the study and a Study Termination eCRF will be completed.

The following is a list of reasons for which subjects may be withdrawn and the date of termination that should be used on the Study Termination eCRF in each situation. This list is not all inclusive:

Termination Reason	Date of Termination
Death	Date of death
Investigative center termination	Date of study close-out visit
Lost to follow-up	Date Stryker termination approval given
Voluntary withdrawal	Date subject notified center of withdrawal
Revision/removal of study device	Date of revision/removal procedure
Study device not implanted	Date of surgery
Surgery not performed	Date Stryker termination approval given

At the time of study surgery it is required that the following components are implanted to be included in the analysis:

- Triathlon Tritanium Femoral Cone Augment or Central Femoral Cone Augment and/or Tibial Cone Augment
- Triathlon TS Femoral Component
- Triathlon TS Universal Tibial Baseplate
- Triathlon TS Tibial Insert or Triathlon PS Tibial Insert

Revision or removal of the Triathlon Tritanium Cone Augments for aseptic loosening constitutes a failure. Revision or removal of all implanted Triathlon Tritanium Cone Augments for any reason requires study termination for the subject.

If revision of the Tibial Insert or the Patellar Component is required during the study, the event does not constitute a failure or study termination.

Patellar component revision at the time of study surgery is optional. However, if the subject requires patellar component revision a Triathlon Patellar Component must be used. If the patellar component is not revised at the time of study surgery and is later revised, it must be revised to a Triathlon Patellar Component. This event is considered a reoperation and does not constitute a failure or study termination.

If the subject fails to return for his/her follow-up appointments, every effort should be made to contact the subject to assess his/her health status. If, after attempting to contact the subject through three documented phone calls and a certified letter, the subject still does not respond, he/she will be considered lost to follow-up. A Study Termination eCRF will be completed only after notifying Stryker of the subject's status and being given approval to terminate.

In the event a subject does not have surgery, Stryker should be contacted to discuss if/when the surgery will be rescheduled. If the surgery is rescheduled more than 4 months from the date of consent, the subject will need to reaffirm participation in the study. All preoperative data will need to be re-collected to be current within 4 months of study surgery. If the surgery is not to be rescheduled or if the subject is no longer considered an appropriate study candidate, a Study Termination eCRF may be completed only after notifying Stryker of the subject's status and **being given approval to terminate**.

When a subject completes the study according to protocol, including the final study evaluation, a Study Termination eCRF will be completed.

5 Study Details

5.1 Study Objectives and Evaluation Schedule

The primary and secondary study objectives, as well as additional data collection are listed on page 2. For the evaluation schedule, please reference page 7.

5.2 Radiographic Outcomes

Radiographs will be taken and collected in the anteroposterior (AP), mediolateral (ML), and merchant or skyline views for the preoperative, 6-week, 6-month, 1-year, 2-year, and 5-year intervals. At the preoperative and 6-week follow-up, a long-standing AP view will be taken. The suggested radiographic technique for the views required is included in Appendix E.

Radiographs will be evaluated by an independent reviewer throughout the course of the study. Parameters for radiographic failures will follow the guidelines that have been set by the Knee Society¹⁰. Radiographic analysis of the tibial component will employ nine zones (Zone 1 – Zone 9) in the AP view and seven zones (Zone 1 – Zone 7) in the lateral view. Radiographic analysis of the femoral component will employ five zones (Zone 1 - Zone 5) in the AP view and nine zones (Zone 1 – Zone 9) in the lateral view. Several parameters will be reviewed by zone, including mechanical alignment, radiolucency, and osteolysis and migration.. Radiolucency in at least 50% of a zone and measuring at least 1 mm in width is defined as radiolucency present. Cases that present with at least 2 mm radiolucency in all zones within a single view will be considered radiographic failures. A migrating or shifting prosthesis with or without disappearance of

radiolucent lines or bone-prosthesis or bone-cement interface may be considered as a possible radiographic failure. This determination will be made by the independent reviewer.

6 Adverse Events

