6.1 Reporting of Adverse Events

The AE reporting requirements for this study are as follows:

- All AEs that meet the definition of serious (see page 27) and occur within the perioperative period (intraoperative to hospital discharge) to 90 days following the date of surgery.
- All AEs related to the operative site, regardless of seriousness or time of occurrence.

On postoperative functional evaluations, investigators and SCs will be prompted to question subjects as to whether they have seen a doctor for any reason, been hospitalized for any reason or have a current impediment to their function.

The following decision tree facilitates identification of AEs for which reporting is required under this study protocol:

Yes

Stryker via AE eCRF

perioperative period to 90 days following date of surgery?

End

General Physical Examination Findings

At screening for inclusion into the study, any clinically significant abnormality should be recorded as a preexisting condition and reported on the Demographics eCRF. From the time of consent forward, any new clinically significant findings or abnormalities that meet the definition of a protocol defined AE must also be recorded and documented as an AE.

Adverse Event Reporting Period

The study period during which AEs must be reported is normally defined as the period from the initiation of any study procedures to the end of the study treatment follow-up. The start of study procedures is considered to be the point of consent. Any AEs which fit the protocol defined reportable events must be reported from the time of consent until study completion.

At each contact with the subject the investigator must seek information on AEs by specific questioning and, as appropriate, by examination. Information on protocol defined AEs should be recorded immediately in the source document and also in the appropriate AE module of the eCRF. All clearly related signs, symptoms and abnormal diagnostic procedure results should be recorded in the source document and grouped under one diagnosis, as appropriate. The clinical course of each event should be followed until resolution or until it is determined at the end of the study that the AE will not resolve.

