For radiographic data, data will be presented according to visits for available parameters. Frequency and percentage will be computed for radiolucency according to visit. Lists will be generated for migration over time. Radiographic failure will be evaluated, where radiographic failure is defined as at least 2 mm radiolucency in all zones within a single view. Radiographic failure due to device migration will be evaluated by the independent reviewer. Documentation of statistical analyses utilizing SAS[®] software version 9.1.3 or higher.

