Appendix E

Suggested Radiographic Technique

Suggested Radiographic Techniqueⁱ

The following views are required preoperatively and at each postoperative interval specified according to the evaluation schedule to enable evaluation of the bone-prosthesis interfaces.

- Long Standing AP
- AP
- ML
- Merchant (30° of flexion)

General Requirements

- A. Appropriate corrections in radiological exposure setting are needed for obese subjects.
- B. At least a 14"x17" sized film should be used.
- C. If the subject is **bilateral** and a view showing both knees is submitted, **two copies of that view are required**.
- D. Both digital and film radiographs are acceptable. **Digital films must be in uncompressed DICOM format.**
- E. A view capturing the complete prosthesis must be submitted to Stryker. Radiographs incompletely displaying components will be rejected.
- F. Each image must have:
 - a. Subject's identification number
 - b. Subject's initials
 - c. Date of radiograph
 - d. Indication of operative side in the study
 - e. Markers for right and left sides, as applicable
 - f. Visit interval

AP

A. Long Standing techniqueⁱⁱ

- The subject should be standing with the study knee in 10° flexion. Both knees should be in the view.
- b. The x-ray beam should be directed vertically to the study knee with 5° to 7° angulation toward the subject's head.
- c. The entire lower extremity, including the ipsilateral and contralateral hip must be visible on the film as shown in Figure 1. The femoral component, the medial

and lateral femoral epicondyles, tibial component and an unobstructed view of the polyethylene tibial insert must be visible on film as well.

- B. Standard technique
 - d. The subject should be supine with the knee in full extension and the leg positioned neutrally. Both knees should be in the view.
 - e. The x-ray beam should be directed vertically to the study knee with 5° to 7° angulation toward the subject's head.
 - f. The femoral component, the medial and lateral femoral epicondyles, tibial component and an unobstructed view of the polyethylene tibial insert must be visible on film as shown below (Figure 2).

Refer to Figure 1 and 2 for an acceptable AP radiographs.

Figure 2. Standard AP View - Acceptable

ML

- A. Standard technique
 - a. The subject should be lying flat on the same side as the study knee. The knee should be flexed 25° to 30°.

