The Stryker Orthopaedics Triathlon TS Tibial Baseplates, Triathlon TS Femoral Components, Triathlon TS Tibial Inserts, Triathlon Tritanium Cone Augments, and/or ancillary component(s) obtained at the time of revision/removal should be placed in neutral buffered formalin. Each specimen container should be carefully labeled with subject initials, operative side, surgeon name and the component(s) included for analysis. Whenever possible, relevant radiographic studies and a clinical summary should be placed on the outside of the shipping container along with the specimen.

All specimens should be placed into a sufficient quantity of 10% formalin for a minimum of 24 hours prior to shipping.

After the specimens have been immersed in 10% formalin for a minimum of 24 hours, they should be transferred to a leak proof container with a quantity of 10% formalin sufficient to keep the specimens moist.

C. Recommendations for Packing and Shipping Explants To Stryker Orthopaedics

Please contact the Triathlon Tritanium Cone Augments Outcomes Study CSM, identified on the Stryker Orthopaedics Contact Sheet, via phone or email once the scheduled revision/removal surgery has been performed in order to notify the study team of the intended revision/removal.

A confirmation with the Product Inquiry (PI) number, including shipping instructions, will be provided by Stryker once the event is reported to Stryker. Please ensure that the provided PI number is marked on the outside of the shipping container.

RESULTS

A report suitable for routine patient care will be provided to each surgeon by request.

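### A knee that loosens and is revised between scheduled films can be missing from the radiographic failure table, because nothing requires its pre-revision film to reach the independent reviewer

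*Combined protocol and SAP*

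**What the plan says.** **Collection.** Section 5.2 sets AP, ML and Merchant or skyline "views for the preoperative, 6-week, 6-month, 1-year, 2-year, and 5-year intervals". Appendix E repeats the rule: "The following views are required preoperatively and at each postoperative interval specified according to the evaluation schedule". Neither place names a film taken between visits or before a revision.

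**Reading.** "Radiographs will be evaluated by an independent reviewer throughout the course of the study". The failure rule is: "Cases that present with at least 2 mm radiolucency in all zones within a single view will be considered radiographic failures". Migration may also count as a possible failure if the independent reviewer so judges.

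**Analysis.** Section 8.4.1: "For radiographic data, data will be presented according to visits for available parameters". Section 8.3 rules out imputation. The Synopsis (Additional Data Collection) plans to compare radiographic stability with published results for other revision systems.

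**Exit from the study.** Section 4.3: "Revision or removal of all implanted Triathlon Tritanium Cone Augments for any reason requires study termination for the subject". The table in that section dates such a termination to the procedure.

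**Films around a revision.** Appendix F, on shipping explants to the sponsor: "Whenever possible, relevant radiographic studies and a clinical summary should be placed on the outside of the shipping container along with the specimen". Section 6.1, on adverse events: "All clearly related signs, symptoms and abnormal diagnostic procedure results should be recorded in the source document". The adverse event form in Appendix G asks sites to send de-identified source documents when device relation is affirmed or uncertain, and Section 7.3 lists radiographs among source documents. None of these places says that the film goes to the independent reviewer.

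**The concern.** In a by-visit table built on available films, knees should not drop out because of the outcome being tabulated. Here they can. Take a cone that is sound on the 1-year film, loosens, and is removed at 18 months with no other cone in place. It contributes one normal reading and then nothing: no 2-year film exists, and the film that led to the revision need not be read against the Section 5.2 zones. The loss is informative and runs in one direction.

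At stake is a descriptive rate, not a hypothesis test. That rate is nevertheless meant for comparison with published results for other revision systems, where an omission favouring the device could mislead.

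**Working it through.** The plan states no radiographic failure rate and no between-visit revision rate, so there is no figure to reproduce. The check is to see whether any text closes the gap, and then to bound the number of knees affected.

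**1. Gaps between postoperative films** (Section 5.2, nominal times; 6 weeks = 42/30.4375 = 1.4 months):
- 6 weeks to 6 months: 6 − 1.4 = 4.6 months
- 6 months to 1 year: 6 months
- 1 to 2 years: 12 months
- 2 to 5 years: 36 months

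The later gaps leave room for loosening and revision between films.

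**2. Does another provision bring the film to the independent reviewer?**
- Appendix F asks for films with the explant only where possible, and lets subjects decline retrieval analysis.
- Section 6.1 places abnormal diagnostic results in the site's source record, which is not an independent zone reading.
- The adverse event form can bring source documents to the sponsor when the event is judged device-related or uncertain.
- Section 5.2 does not bar reading such films, but no sentence requires their submission or reading.

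The film may therefore arrive and may be read, but the plan does not secure either.

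**3. Upper bound on knees affected by 2 years.** Inputs:
- N = 145 (Section 8.4.2), taking all as followed.
- Aseptic cone revision rate q: 1.2% (100% − 98.8% expected success, Section 8.4.2), 2.8% (100% − 97.2% reference) and 5.3% (100% − 94.7%, the non-inferiority bound in Section 8.1.5).
- Share s of those knees with no failing scheduled film before revision: not in the documents, so an assumed range of 25% to 100%.

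Knees missing from the table = 145 × q × s:

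| s (assumed) | q = 1.2% | q = 2.8% | q = 5.3% |
|---|---|---|---|
| 25% | 0.43 | 1.02 | 1.92 |
| 50% | 0.87 | 2.03 | 3.84 |
| 100% | 1.74 | 4.06 | 7.68 |

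The bottom row is the upper bound at each rate. It also assumes that every pre-revision film would meet the strict rule (at least 2 mm in all zones of a view) or be judged a migration failure.

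**4. Chance that the situation arises at all.** P(at least one aseptic cone revision) = 1 − (1 − q)^145, which is 0.83 at 1.2% and 0.98 at 2.8%. This is the chance of a revision, not of an omitted film.

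**5. Effect on the primary count.** Sections 8.1.1 and 8.1.4 define failure as revision or removal of a cone for aseptic loosening. No film reading enters that definition, so the change in the count is 0.

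**The case against.** The strongest reply is that the revised knees are not hidden. Operative-site events are reportable at any time (Section 6.1), including between visits (Section 6.4), and revisions within 24 hours (Section 6.3). Aseptic cone revision is the primary endpoint, and Kaplan-Meier curves cover cone revision (Section 8.1.5) and all-cause revision (Section 8.2.2). A descriptive table of knees still in place, read beside those curves, is a legitimate presentation. This stands, and it limits the consequence. It does not make the by-visit rate suitable for comparison with published radiographic results.

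Three stronger readings are tempting, and the documents support none of them.

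- **That such a knee is never read in its failed state.** A scheduled film before revision is read and may already show failure, and the routes in Appendix F and the adverse event form may supply a later one. Delivery to the sponsor does not show that the independent reviewer is bypassed, because Appendix E sends scheduled films to the sponsor too. The lack of an unscheduled film in the Appendix G visit list shows nothing either, as that list has no radiograph form at all. The background in Section 1.1 places aseptic failures at six months and by 25 months, near scheduled films and not clearly between them.
- **That under-counting is established and can be stated as a rate.** Without a documented radiographic failure rate, any pair of reported and true percentages would be invented.
- **That the missing film threatens the primary verdict through the septic or aseptic label.** One label can matter: at n = 100, the 90% Clopper-Pearson lower bound is 95.3% with one failure and 93.8% with two, either side of 94.7%. But the Section 5.2 criteria (alignment, radiolucency, osteolysis, migration) describe loosening and not infection, and Section 11.2 notes that infection can cause loosening. A film reading cannot settle the label. Nor is the investigator's view the only scrutiny: the sponsor screens reported revisions for a product inquiry (Section 6.3), formally investigates those entered in that system (Section 6.5) and analyses explants (Section 6.3.2). None of these is described as adjudication of cause, but that is a separate matter.

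**Conclusion.** The point holds in a limited form. The plan ties collection to fixed visits, ends participation at full cone removal, tabulates by visit without imputation, and does not require a pre-revision film to reach the independent reviewer. Radiographic failure can therefore be under-counted, and any such error favours the device. By 2 years the under-count is at most about 1.7 of 145 knees at the planned rate and 4.1 at the reference rate. Those bounds assume full follow-up, no failing scheduled film before any revision, and a pre-revision film that always meets the failure rule. The true number is unknown and probably lower. The radiographic output is descriptive, and the primary count does not depend on it. This is a worthwhile, inexpensive improvement and not a flaw in the main analysis.

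**What to change.** **Section 5.2.** Require sites to submit the last AP and ML films already taken in routine care before revision or removal of a cone, femoral component or tibial baseplate. Have the existing independent reviewer read them by the same zones and failure rule, blinded to the reported cause.

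**Section 8.4.1.** Keep the by-visit table. Add cumulative radiographic failure to 2 years, counting any scheduled or pre-revision reading, with its denominator stated, and show the number of knees revised for aseptic loosening beside it. For each cone revision, list the reviewer's reading next to the investigator's reported cause. Label this as supporting information on loosening only, not as adjudication of septic versus aseptic cause.

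**Cost.** A few existing films to submit and read: about 2 to 4 for aseptic cone loosening by 2 years at the plan's rates, plus those for other revisions, for which the documents give no rate. Protocol and analysis wording must change. There is no new imaging, visit or reader, and no change to patient management. The drawbacks are minor site effort and a radiographic failure rate that may look slightly worse.
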